6.2 Physical/Neurological Examination Result

For the results of the physical/neurological examination, the analysis presents the proportion of subjects who were normal at Screening visit (Visit1) and changed to abnormal at End of Study (Table 28).

Table 28. Physical/Neurological Examination Result

Investigational arm (N=xx)		Control arm (N=xx)	
n (%)	Normal → Abnormal, n (%)	n (%)	Normal → Abnormal, n (%)
mITT			
Physical examination	xx	xx (xx.xx)	xx
Neurological examination	xx	xx (xx.xx)	xx
PP			
Physical examination	xx	xx (xx.xx)	xx
			xx (xx.xx)

Neurological examination	xx	xx (xx.xx)	xx	xx (xx.xx)
Safety				
Physical examination	xx	xx (xx.xx)	xx	xx (xx.xx)
Neurological examination	xx	xx (xx.xx)	xx	xx (xx.xx)

6.3 Chemistry/Electrolyte/Complete Blood Count

The analysis presents the proportion of subjects who showed the chemistry/electrolyte/complete blood count result of “Normal” or “Abnormal NCS” at Baseline visit (Visit2) and changed to “Abnormal CS” at End of Study (Table 29).

Table 29. Chemistry/Electrolyte/Complete Blood Count

	Investigational arm (N=xx)		Control arm (N=xx)	
	n	Normal or Abnormal NCS → Abnormal CS, n (%)	n	Normal or Abnormal NCS → Abnormal CS, n (%)
mITT				
Chemistry				
T-bilirubin	xx	xx (xx.xx)	xx	xx (xx.xx)
Alkaline phosphatase	xx	xx (xx.xx)	xx	xx (xx.xx)
AST	xx	xx (xx.xx)	xx	xx (xx.xx)
ALT	xx	xx (xx.xx)	xx	xx (xx.xx)
Creatinine	xx	xx (xx.xx)	xx	xx (xx.xx)
Albumin	xx	xx (xx.xx)	xx	xx (xx.xx)

Electrolyte

Sodium	xx	xx (xx.xx)	xx	xx (xx.xx)
Potassium	xx	xx (xx.xx)	xx	xx (xx.xx)
Chloride	xx	xx (xx.xx)	xx	xx (xx.xx)

Complete blood count

WBC	xx	xx (xx.xx)	xx	xx (xx.xx)
ANC	xx	xx (xx.xx)	xx	xx (xx.xx)
Hemoglobin	xx	xx (xx.xx)	xx	xx (xx.xx)
PLT	xx	xx (xx.xx)	xx	xx (xx.xx)

PP**Chemistry**

T-bilirubin	xx	xx (xx.xx)	xx	xx (xx.xx)
Alkaline phosphatase	xx	xx (xx.xx)	xx	xx (xx.xx)
AST	xx	xx (xx.xx)	xx	xx (xx.xx)
ALT	xx	xx (xx.xx)	xx	xx (xx.xx)
Creatinine	xx	xx (xx.xx)	xx	xx (xx.xx)
Albumin	xx	xx (xx.xx)	xx	xx (xx.xx)

Electrolyte

Sodium	xx	xx (xx.xx)	xx	xx (xx.xx)
Potassium	xx	xx (xx.xx)	xx	xx (xx.xx)
Chloride	xx	xx (xx.xx)	xx	xx (xx.xx)

Complete blood count

WBC	xx	xx (xx.xx)	xx	xx (xx.xx)
ANC	xx	xx (xx.xx)	xx	xx (xx.xx)
Hemoglobin	xx	xx (xx.xx)	xx	xx (xx.xx)

PLT	xx	xx (xx.xx)	xx	xx (xx.xx)
Safety				
Chemistry				
T-bilirubin	xx	xx (xx.xx)	xx	xx (xx.xx)
Alkaline phosphatase	xx	xx (xx.xx)	xx	xx (xx.xx)
AST	xx	xx (xx.xx)	xx	xx (xx.xx)
ALT	xx	xx (xx.xx)	xx	xx (xx.xx)
Creatinine	xx	xx (xx.xx)	xx	xx (xx.xx)
Albumin	xx	xx (xx.xx)	xx	xx (xx.xx)
Electrolyte				
Sodium	xx	xx (xx.xx)	xx	xx (xx.xx)
Potassium	xx	xx (xx.xx)	xx	xx (xx.xx)
Chloride	xx	xx (xx.xx)	xx	xx (xx.xx)
Complete blood count				
WBC	xx	xx (xx.xx)	xx	xx (xx.xx)
ANC	xx	xx (xx.xx)	xx	xx (xx.xx)
Hemoglobin	xx	xx (xx.xx)	xx	xx (xx.xx)
PLT	xx	xx (xx.xx)	xx	xx (xx.xx)

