7.2. Investigational arm

	Screening	Baseline Visit ¹	Treatment					End of Treatment ⁷	Treatment completion to End of Study
Weeks (w)	-2w ~ 0d n-a	0 n-a	1w	2w	4w	8w	12w ~ (Every 4w)	40w ~ 52w	~ 24month (Every 2month) ±2w
			±4d	±4d	±1w	±2w	±2w	±2w	
Consent	O								
Randomization		O							
Medical history	O								
Physical Exam	O		O	O	O	O	O	O ⁷	
Neurologic exam	O		O	O	O	O	O	O ⁷	
Sputum AFB smear	O ⁵	O ⁵	O	O	O	O	O	O	O
TB culture (solid)	O ⁵	O ⁵	O	O	O	O	O	O	O
TB culture (liquid)	O ⁵	O ⁵	O	O	O	O	O	O	O
Genotypic DST	If available								
Phenotypic DST ²	With first/reverted cultured M.TB								
LZD, Delamanid resistance examination	If needed (please see the protocol section 9.0)								
Chest X-ray (CXR)	O ⁵	O ⁵	O ⁸	O ⁸	O	O	O	O	O
Chemistry, Electrolyte	O ⁵	O ⁵	O	O	O	O	O	O ⁷	
Complete blood count	O ⁵	O ⁵	O	O	O	O	O	O ⁷	
ECG	O ⁵	O ⁵	O	O	O	O	O	O ⁷	
Urine HCG ³	O	O	O	O	O	O	O	O ⁷	
HIV, HBV ⁴		O ⁵							
Optic test	O	O	O	O	O	O	O	O ⁷	
Compliance of drug intake			O	O	O	O	O	O ⁷	
Adverse drug reaction			O	O	O	O	O	O ⁷	
Other medication ⁶	O	O	O	O	O	O	O	O ⁷	

¹Administration of anti-TB regimen can begin at baseline visit since drug-resistant TB must be treated immediately.

²Drug susceptibility test for isoniazid, rifampicin, ethambutol, pyrazinamide, streptomycin, kanamycin, amikacin, capreomycin, ofloxacin, levofloxacin, moxifloxacin, prothionamide, cycloserine, and para-aminosalicylic acid (omit for patients with results provided already).

³Only for childbearing age (the blood HCG test result can be extracted).

⁴Study drugs can be administered before the obtaining of results since eligibility is not determined by these results.

⁵Could be skipped if previous tests except ECG were been done within four weeks. In case of ECG, within 1week.

⁶Check prohibited drugs for exclusion criteria at screening visit, and check immunosuppressants including steroids after enrollment.

⁷End of treatment visit will be determined by the time of culture conversion. Omit test after end of treatment (EOT) visit.

⁸Could be skipped if previous CXR test was performed within 2 weeks

Confidential

MDR-END v14.0, 20Mar2020

8. Screening and Procedures

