8.4. Study Visits

- Subjects will visit for study at 1 week, 2 weeks and 4 weeks after enrollment, and then every four weeks until 12 months(52 weeks), afterwards every 2 months until the end of treatment (EOT). The time of EOT is 40 or 52 weeks for the Investigational arm and will be determined individually for control arm according to the standard of care treatment.
- Subjects in the investigational arm will visit every 2 months after EOT even if it is before 12 months(52 weeks).

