8.4.2. Follow-up visits after EOT (Investigational arm only)

- Sputum AFB smear microscopy and MTB culture on liquid and solid media
- CXR

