3.7 Safety Analysis

The safety analysis evaluates subjects enrolled in this clinical trial and administered the study drug at least one time.

1) Adverse Events

- The analysis obtains the 95% confidence interval of the proportion of the subjects who have experienced one or more adverse event within each arm and performs the Chi-Square Test or Fisher's Exact Test to compare the treatment groups.
- It compares the occurrence rate of adverse drug reactions of the two arms using the Chi-square test or Fisher's exact test.
- It summarizes the number of adverse events of each arm.
- It summaries the number of expressions of five items (seriousness, severity, relation, action taken, and outcome) for each arm.
- The classification of adverse events by body system is organized according to the SOC (System Organ Class) and PT (Preferred Term) of MedDRA system.
- It describes the details such as demographic information, event date, end date, severity, relation, action taken, and outcome for the subjects who reveal serious adverse events.

2) Physical/Neurological Examination Result

- For the results of the physical/neurological examination, the analysis presents the proportion of subjects who were normal in screening visit (Visit1) and changed to abnormal at the final visit.

3) Chemistry/Electrolyte/Complete Blood Count Result

- The analysis presents the proportion of subjects who showed the chemistry/electrolyte/complete blood count result of "Normal" or "Abnormal NCS" at the baseline visit (Visit2) and changed to "Abnormal CS" at the final visit.

4) Concomitant Medication

- The analysis classifies the concomitant medication using the ATC (Anatomical Therapeutic Chemical)

Code presents it for each arm.

4. Subjects

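### SAP Tables 28 and 29 measure safety shifts at End of Study, where the investigational arm has none of the tests scheduled, and SAP 3.7 names a different, undefined visit

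*Combined protocol and SAP*

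**What the plan says.** **SAP, table sections.** SAP 6.2 (Table 28) reports the proportion of participants who "were normal at Screening visit (Visit1) and changed to abnormal at End of Study (Table 28"). SAP 6.3 (Table 29) reports laboratory results that were normal or not clinically significant at baseline and had become clinically significant "at End of Study (Table 29"). Both shells have columns for both arms, in the mITT, PP and Safety groups.

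**SAP, methods section.** For the same physical and neurological analysis, SAP 3.7 counts those who "were normal in screening visit (Visit1) and changed to abnormal at the final visit". Its laboratory bullet also ends at the final visit. That term is not defined.

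**Protocol, investigational arm.** Protocol 8.4 says: "The time of EOT is 40 or 52 weeks for the Investigational arm and will be determined individually for control arm". Footnote 7 of the schedule in protocol 7.2 says "Omit test after end of treatment (EOT) visit". Protocol 8.4.2, headed "Follow-up visits after EOT (Investigational arm only"), lists only sputum smear and culture and chest X-ray.

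**Protocol, control arm.** The schedule in protocol 7.1 marks chemistry, electrolytes and blood count up to End of Treatment and leaves the 24-month cell blank. Its footnote 7 adds that when the two visits are the same, the End of Treatment tests are done. Physical examination is marked at the 24-month visit. Neurological examination is marked at screening only.

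**The concern.** A shift table needs a value at each end. Here the SAP picks a closing visit at which the investigational schedule provides none of the tests. These two tables are the SAP's only by-parameter display of how laboratory and examination findings changed during the trial, so their closing visit should be one that the schedule supplies in both arms.

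Two things are at stake. First, read literally, the tables give no between-arm comparison from scheduled data. Second, the SAP names the closing visit in two ways. Whoever programs the tables would have to choose a meaning for the final visit after the fact, although SAP section 1 says the plan exists to state the analyses clearly and prevent unplanned ones.

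**Working it through.** The plan states no figure to reproduce. The check compares the last scheduled occurrence of each test (schedules in protocol 7.1 and 7.2) with the closing visit in SAP 6.2 and 6.3.

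| Test | Investigational: last scheduled | Control: last scheduled | Scheduled value at End of Study? |
|---|---|---|---|
| Chemistry, electrolytes | End of Treatment | End of Treatment | Investigational: no. Control: only if End of Treatment is the 24-month visit |
| Blood count | End of Treatment | End of Treatment | Same as above |
| Physical examination | End of Treatment | End of Study | Investigational: no. Control: yes |
| Neurological examination | End of Treatment | Screening | No, in either arm |

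**Parameters affected.** Table 29 lists 6 chemistry + 3 electrolyte + 4 blood count = 13 parameters. In the investigational arm 0 of 13 has a scheduled End of Study value.

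**Can the two visits coincide in the investigational arm?** No. End of Treatment is week 40 or 52. Taking 24 months as about 104 weeks, End of Study falls 104 − 52 = 52 to 104 − 40 = 64 weeks later.

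**Can they coincide in control?** Yes. Protocol 5.1.2 recommends 20 to 24 months of treatment, so End of Treatment can fall on the 24-month visit. Let f be the share of control participants for whom it does. The documents do not give f, so it may lie anywhere from 0 to 1:

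- f = 0: Table 29 has no scheduled closing value in either arm.
- 0 < f < 1: control shows only those treated up to 24 months, and the investigational arm is empty.
- f = 1: control is filled and the investigational arm is empty.

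No value of f gives a between-arm comparison.

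**Control neurological row of Table 28.** The only scheduled examination is at screening, and the control on-treatment list in protocol 8.4.1 has physical examination only. No choice of closing visit fills this row from scheduled data.

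**Related inconsistency in the control tests.** The control on-treatment list in protocol 8.4.1 omits albumin and electrolytes, which are 1 + 3 = 4 of the 13 Table 29 parameters. The schedule in protocol 7.1 has a combined chemistry and electrolyte row at those visits. Moving the closing visit to End of Treatment yields these four parameters in control only if the schedule row governs.

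**Would a worst on-treatment value compare like with like?** Investigational on-treatment visits are at weeks 1, 2 and 4 and then every 4 weeks: 3 + 9 = 12 to week 40, or 3 + 12 = 15 to week 52. Control is treated for 20 to 24 months against 9 to 12, which is between 20/12 ≈ 1.7 and 24/9 ≈ 2.7 times as long. Control would have more time in which to record a worst value.

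**The case against.** The strongest reply has three parts.

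**The tables need not be empty.** SAP 3.7 is the methods text. If its final visit means the last visit with a result, Table 29 can be filled in both arms. Even on the End of Study reading, some control laboratory values may exist through footnote 7 of the control schedule, and the control physical examination is scheduled at 24 months. This stands. A reader might infer that the tables cannot be produced at all; the documents do not support that. But 3.7 does not say last visit with a result. For an investigational participant who completes follow-up, the literal final visit is the 24-month visit, which has no laboratory tests. The favourable reading has to be written down.

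**The tables would not show off-treatment recovery.** A reader might infer from the 52 to 64 week gap that the tables would present values taken long after the drugs stopped. The schedules do not support that either: no off-treatment laboratory test is scheduled in either arm. Any scheduled End of Study laboratory values would be control end-of-treatment values. Off-treatment values could come only from unscheduled tests.

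**Toxicity is captured elsewhere.** A reader might also infer that on-treatment cytopenia, liver injury or neuropathy would go unreported. It would not. Adverse events include abnormal laboratory findings (protocol 11.1), are graded by CTCAE, are collected regardless of severity (protocol 11.2), and are summarised by arm in SAP Tables 23 to 26. Events of grade 3 and higher are a secondary outcome (protocol 5.3). Protocol 8.5 also requires location, severity and relationship to be documented for neurological events. This part stands in full and limits the importance of the point.

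**Conclusion.** The closing visit in SAP 6.2 and 6.3 is the wrong rule for this schedule, and it conflicts with SAP 3.7. Under the End of Study rule:

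- Investigational arm: no scheduled laboratory, physical or neurological value (0 of 13 Table 29 parameters, 0 of 2 Table 28 rows).
- Control laboratory values: only for participants whose End of Treatment is the 24-month visit, a selected subset of unknown size.
- Control neurological row: cannot be filled from any scheduled visit, whichever closing visit is chosen.

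This rests on the schedules as printed and on scheduled tests only; unscheduled tests could add values. The consequence is limited. Both tables are descriptive, and no efficacy conclusion or adverse event analysis depends on them. The correction is worth making because it is cheap and makes the tables producible, apart from the control neurological row.

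**What to change.** 1. In SAP 3.7, 6.2 and 6.3, replace both End of Study and final visit with one defined endpoint: the End of Treatment visit, or the last on-treatment assessment if treatment stops early. The second clause keeps in the table those who leave before a planned End of Treatment.
2. In Table 28, report the neurological shift for the investigational arm only, and state that control has no scheduled neurological examination after screening.
3. Optionally add a worst on-treatment column as a descriptive supplement, with a note that treatment lasts 9 to 12 months in one arm and 20 to 24 in the other. It should not replace the single-visit comparison.
4. Reconcile the control on-treatment list in protocol 8.4.1, which omits albumin and electrolytes, with the chemistry and electrolyte row of the schedule in protocol 7.1. If those tests were not done in control, say so in Table 29.

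Items 1 to 3 cost SAP wording and table programming, with no new visits or tests. Item 4 is a protocol clarification, and the availability of those four parameters in control should be confirmed before the table is programmed.

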6.4 Concomitant Medication

Concomitant medication during the study period will be classified using the ATC (Anatomical Therapeutic Chemical) Code and presented for each arm (Table 30).

Table 30. Concomitant Medication (Unit: Persons)

ATC code	Investigational arm (N=xx)	Control arm (N=xx)	Total (N=xx)
mITT			
XXX, n (%)	xx (xx.xx)	xx (xx.xx)	xx (xx.xx)
XXX, n (%)	xx (xx.xx)	xx (xx.xx)	xx (xx.xx)
XXX, n (%)	xx (xx.xx)	xx (xx.xx)	xx (xx.xx)
PP			
XXX, n (%)	xx (xx.xx)	xx (xx.xx)	xx (xx.xx)
XXX, n (%)	xx (xx.xx)	xx (xx.xx)	xx (xx.xx)
XXX, n (%)	xx (xx.xx)	xx (xx.xx)	xx (xx.xx)
Safety			
XXX, n (%)	xx (xx.xx)	xx (xx.xx)	xx (xx.xx)
XXX, n (%)	xx (xx.xx)	xx (xx.xx)	xx (xx.xx)
XXX, n (%)	xx (xx.xx)	xx (xx.xx)	xx (xx.xx)

7. Conclusion

7.1 Efficacy

The analysis describes the statistical analysis results.

7.2 Safety

The analysis describes the statistical analysis results.
